Subjects who permanently discontinue IP early should complete an End of Treatment Visit (Section 8.3.3) as soon as possible followed by a Post-End of Treatment Visit (Section 8.4.1) 1 month after the End of Treatment Visit. Subjects should then continue on study and follow the protocol-defined schedule of events, through Month 24. The subject has the option to continue on study-supplied XOI during this time. Although all assessments are encouraged, at a minimum, it is requested that collection of AEs and collection of a blood sample for Analytes 1 (see Table 1) occur. Alternatively, if the subject does not agree to this option, a modified follow-up including, eg, regular telephone contacts or a contact at Month 24, should be arranged, if agreed to by the subject and in compliance with local data privacy laws/practices. Subjects who do not wish to continue on study after discontinuing IP should complete an End of Study Visit (Section 8.4.2) 1 month after treatment discontinuation.

If IP is permanently discontinued prior to the Month 6 study visit, then gout flare prophylaxis should also be discontinued.

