6.9.1. Clinical Safety Laboratory Assessments

Blood and urine samples will be collected for clinical safety laboratory tests (hematology, serum chemistry, and urinalysis) and will be tested by a central laboratory. Any clinical safety laboratories results post-Baseline that are considered possibly significant may be repeated (see [Section 6.12](#)).

See [Table 1](#) for a list of clinical safety laboratory tests.

Table 1: Clinical Safety Laboratory Tests

Hematology:
 
 • Hematocrit • Hemoglobin • Mean corpuscular hemoglobin • Mean corpuscular hemoglobin concentration • Mean corpuscular volume • Platelet count • Red blood cell count • Red blood cell morphology • White blood cell count with differential 
Urinalysis:
 
 • Appearance • Bilirubin • Color • Glucose • Ketones • Nitrite • Occult blood • pH • Protein • Specific gravity • Urobilinogen • Microscopic examination of sediment including uric acid crystals 
Additional urine analyses:
 
 • Creatinine • Total protein 	
Serum Chemistry:
 
Analytes 1
 
 • Blood urea nitrogen • Creatinine (enzymatic method) • Glucose • Uric acid^a 
Analytes 2
 
 • Albumin • Calcium • Carbon dioxide • Chloride • Phosphorus • Potassium • Sodium • Total cholesterol • Triglycerides 
Analytes 3
 
 • Alkaline phosphatase • Alanine aminotransferase • Aspartate aminotransferase • Total bilirubin • Creatine kinase 
Pregnancy and fertility testing
 
 • Human chorionic gonadotropin^b • Follicle-stimulating hormone^c
---	---

^a Serum uric acid (sUA) will be used for efficacy analyses. All study personnel, except for those defined in Section 5.5, will be blinded to sUA results collected after Baseline through database lock.

^b At Screening Visit 2 for all females and again at Month 12 for all females except those who are surgically sterile or not of childbearing potential as confirmed by the Screening Visit 2 follicle-stimulating hormone test.

^c At Screening Visit 2. Only for females with 12 months of spontaneous amenorrhea who are not surgically sterile.

Estimated CrCl at each visit will be calculated by the Cockcroft-Gault formula using ideal body weight (based on height measured at Screening) as follows:

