9.4.2.2. Renal-Related Outcomes

The following renal-related outcomes will be reported as both incidence proportions and exposure-adjusted incidence rates:

- Incidence of sCr elevation ($\geq 1.5 \times$ Baseline).
- Incidence of subjects meeting criteria (eg, based on sCr or eCrCl criteria) for treatment discontinuations.
- Incidences of renal-related and kidney stone TEAEs and SAEs.
- Prevalence of contributing factors to renal SAEs as adjudicated by the REAC.

The proportion will be calculated as the number of subjects with an outcome of interest (ie, unique subjects) during the study divided by the total number of subjects in that treatment group. The 95% CIs will be calculated based on the Wilson Score method.

The on-treatment exposure-adjusted incidence rates for an outcome of interest will be calculated as the number of subjects with that outcome of interest during the Treatment Period divided by the total duration of treatment in each treatment group (ie, “on-treatment” analysis). Similarly, the on-study exposure-adjusted incidence rates will be calculated as the number of subjects with outcome of interest during the study divided by the total duration of study in each treatment group (ie, “on-study” analysis). Exposure-adjusted incidence rates and associated exact CIs

based on the Poisson distribution will be calculated for each treatment group and reported per 100 patient-years.

Similar exposure-adjusted analysis will also be performed with the number of events as the numerator dividing by on-treatment or on-study exposure as described above.

Estimates of treatment differences with corresponding 95% CIs will be calculated. The appropriate approaches may depend on the number of events observed during blinded data review and will be detailed in the SAP prior to database lock.

Additional assessments may include the proportion of subjects who require dialysis, those who advance in their chronic kidney disease, those who have persistent decreases in eCrCl, and those who have persistent sCr elevations.

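### The creatinine-elevation endpoint is divided by all subjects and all study time, with no rule limiting either to follow-up in which creatinine was measured

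*Combined protocol and SAP*

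**What the plan says.** Protocol section 3.2.1 sets the creatinine-elevation endpoint over the whole study period, not only the time on IP. Section 9.4.2.2 then gives three summaries for each renal outcome:

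- **Proportion:** unique subjects with the outcome "divided by the total number of subjects in that treatment group".
- **On-study rate:** the "number of subjects with outcome of interest during the study divided by the total duration of study in each treatment group".
- **On-treatment rate:** the "number of subjects with that outcome of interest during the Treatment Period divided by the total duration of treatment in each treatment group".

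The rates are repeated with event counts as numerator. The choice of method for the treatment difference is left to the SAP, and no SAP text on this appears in the documents reviewed.

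After IP is stopped, the default in section 5.3.2.1.2 is to keep the visit schedule; "at a minimum, it is requested that collection of AEs and collection of a blood sample for Analytes 1 (see Table 1) occur". Analytes 1 includes creatinine (Table 1). For a subject who does not agree to this, "a modified follow-up including, eg, regular telephone contacts or a contact at Month 24, should be arranged". Section 8.4 repeats that option. Neither form of contact requires a blood draw.

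Section 9.4.2.3 states event times and censoring for MACE. Section 9.4.2.2 states neither for the renal outcomes.

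**The concern.** A creatinine of at least 1.5 times Baseline can be seen only when blood is drawn. A subject on telephone follow-up cannot have the event recorded, yet stays in the denominator of the proportion as event-free. If telephone months count toward study duration, they also enter the on-study rate as time at risk when no event could be observed. Subjects who leave the study early add no later study time, but they too count as event-free in the proportion.

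Safety is the primary objective, and section 1.3 puts the focus on renal safety. For change in eCrCl, section 9.4.2.1 recognises that subjects may stop early because renal function is worsening, and it plans multiple imputation with a missing-not-at-random sensitivity analysis. The creatinine-elevation outcome has no counterpart: missing creatinine is read as no elevation. If lesinurad has more unsampled follow-up than placebo, a real excess would be understated.

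**Working it through.** **The plan's own safety figure.** The only safety sizing figure is the 95% CI half-width for eCrCl change: 1.96 × 10 × √(2/300) = 1.60 mL/min, which matches the stated ±1.6. No figure is given for the renal incidence outcomes.

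**Inputs from the documents.** 300 subjects per arm; 24 months of 28 days = 672 days.

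**Assumptions (none is in the documents).** Constant hazard; 30% of lesinurad and 20% of placebo subjects stop IP at Month 8; 40% of stoppers have no later creatinine; all of these stay on study by telephone.

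**Formulae.** Let R be the true 24-month risk and h = −ln(1 − R)/24 per month. The unsampled share is f = (share stopping) × (share of stoppers unsampled), so f = 0.30 × 0.40 = 0.12 for lesinurad and 0.20 × 0.40 = 0.08 for placebo. Observed risk = (1 − f)R + f(1 − e^(−8h)).

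**Equal true risk, 15% in both arms.** 1 − e^(−8h) = 0.0527.
- Lesinurad: 0.88 × 0.15 + 0.12 × 0.0527 = 13.8%.
- Placebo: 0.92 × 0.15 + 0.08 × 0.0527 = 14.2%.
- Difference −0.4 points, ratio 0.97. The on-study rate ratio is the same, because every subject contributes 672 days.
- With 35% against 20% stopping and 50% unsampled (f = 0.175 and 0.10): 13.3% against 14.0%, difference −0.7 points, ratio 0.95.

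**True risks 20% and 12%.** The risks to Month 8 are 0.0717 and 0.0417.
- Lesinurad: 0.88 × 0.20 + 0.12 × 0.0717 = 18.5%.
- Placebo: 0.92 × 0.12 + 0.08 × 0.0417 = 11.4%.
- The true 8.0 points appear as 7.1, and the ratio of 1.67 as 1.62.

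**Ending unsampled subjects' time at the last creatinine.** Mean months are 0.88 × 24 + 0.12 × 8 = 22.08 for lesinurad and 0.92 × 24 + 0.08 × 8 = 22.72 for placebo. The rate ratios become (0.1383/22.08)/(0.1422/22.72) = 1.00 and (0.1846/22.08)/(0.1137/22.72) = 1.67. If time also ends at first event, the second becomes the hazard ratio, ln(0.80)/ln(0.88) = 1.75.

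**A different model for stop times.** With stop times uniform over 24 months, hazards of 0.15 and 0.10 per year, 30% against 20% stopping and half of stoppers unsampled, a simulation gives a risk difference falling from 7.3 to 6.4 points. The lesinurad rate is 13.1 per 100 patient-years with full sampling, 12.2 as planned on-study, and 13.1 with time ended at the last creatinine. With 40% against 20% stopping and all stoppers unsampled, 7.4 points fall to 4.4. With no unsampled stoppers there is no bias.

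**Direction between arms.** It follows unsampled time, not the number of stoppers. In the Month 8 model, let 30% of lesinurad subjects stop with 20% of them unsampled (f = 0.06), and 20% of placebo subjects stop with 40% unsampled (f = 0.08). Equal 15% risks then appear as 14.4% against 14.2%, ratio 1.01, so the arm with more stoppers looks slightly worse.

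**Risk that rises after stopping.** Let the hazard triple after Month 8, with risks of 15% and 10% in subjects who do not stop, and the first set of shares. A stopper's 24-month risk is 1 − e^(−56h), or 31.6% and 21.8%.
- True: 0.70 × 15% + 0.30 × 31.6% = 20.0%, and 0.80 × 10% + 0.20 × 21.8% = 12.4%; difference 7.6 points.
- As planned: 16.8% and 10.9%; difference 5.9 points.
- Censored at the last creatinine: 18.4% and 11.5%; difference 6.8 points.

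**The case against.** The strongest objection is that the plan already has a summary without this flaw. The on-treatment rate excludes time after IP stops, including all telephone time. That stands, and it rules out saying that every planned rate is diluted. It does not answer the concern, because the endpoint covers the whole study period and this rate does not describe risk off IP. Its wording also needs tidying: the numerator refers to the Treatment Period, which section 8.3 runs to Month 24, while the denominator is duration of treatment.

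Second, telephone contact is only the fallback. Stoppers are asked to keep visits with creatinine drawn, and sections 8.3.3 and 8.4.1 also collect it at the End of Treatment and Post-End of Treatment Visits. A rise that prompted stopping would normally be in the numerator already. This limits the size but does not remove the gap.

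Third, a reader might infer that risk is necessarily understated most in the arm with more IP stoppers. The documents do not support that, since stoppers who keep visits are still sampled, and the calculation above gives a counterexample.

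Fourth, a reader might extend the point to every renal outcome. "Incidence of subjects meeting criteria (eg, based on sCr or eCrCl criteria) for treatment discontinuations" hardly applies once IP has been stopped for good, and renal adverse events can be reported by telephone.

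Fifth, the distortion is small against sampling error. With 300 per arm the 95% half-width is 1.96 × √(2 × 0.15 × 0.85/300) = 5.7 points at 15% in both arms, and 5.8 points at 20% against 12%. The main safety estimands are the eCrCl changes, which have their own missing-data analyses. This bears on priority. But the error is systematic, and in the comparison it runs toward no harm whenever lesinurad has more unsampled time.

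**Conclusion.** The concern holds in a limited form. For creatinine of at least 1.5 times Baseline over the study period, the stated proportion counts subjects who can no longer be observed as event-free. The on-study rate is diluted as well if telephone time counts as study duration; the text does not say whether it does, so that part rests on a reading. The downward bias within each arm does not depend on which arm has more stoppers. Bias toward no harm between arms requires a larger share of unsampled time on lesinurad.

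Under the illustrative shares the loss is about 0.9 of 8.0 points, or a ratio of 0.97 where the truth is 1.00. It grows to 1.7 of 7.6 points if risk triples after stopping. All stopping shares, unsampled shares and risks are assumptions. The point should be settled before database lock, but it does not threaten the main eCrCl analysis.

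**What to change.** In the SAP, for creatinine of at least 1.5 times Baseline and any other creatinine-defined outcome assessed off IP:

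1. End on-study time at risk at the first event or the last central creatinine, whichever comes first.
2. Report cumulative incidence at Month 24, with death as a competing event, and the between-group difference with its 95% CI.
3. Keep the crude proportion as a descriptive line.
4. Tabulate by arm the number of subjects with follow-up time without creatinine, and its duration.
5. State whether telephone follow-up counts as study duration, and align the numerator and denominator of the on-treatment rate.

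The cost is SAP wording and one time-to-event dataset of the kind already needed for MACE; visits and data collection do not change. Intervals will be slightly wider. Censoring at the last creatinine reduces the bias but does not remove it if loss of sampling is related to later renal risk: in the tripled-risk example it recovers 6.8 of the true 7.6 points, against 5.9 as planned.

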9.4.2.4. General Safety

All AEs will be coded and tabulated by Medical Dictionary for Regulatory Activities (MedDRA) System Organ Class and preferred term. Similar methods will be applied for estimating proportions and exposure-adjusted incidence rates (ie, on-study and on-treatment exposure-adjustment) of TEAE, SAEs, and TEAEs leading to permanent discontinuation of IP, as described in [Section 9.4.2.2](#).

Associated laboratory parameters such as hepatic profile, renal function, serum chemistry, hematology, and urinalysis values will be grouped and presented together. Individual subject values will be listed and values outside of the standard reference range will be flagged. Marked abnormalities meeting RCTC version 2.0 grading will also be noted. Shift tables and analyses of changes from Baseline will be included.

The change from Baseline for each of the vital signs variables will be summarized.

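### Event-count exposure-adjusted rates appear to inherit exact Poisson intervals, which are too narrow per arm when events recur often within subjects

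*Combined protocol and SAP*

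**What the plan says.** Section 9.4.2.2 of the protocol describes two kinds of exposure-adjusted rate.

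- **Subject-count rate.** The on-treatment version is "calculated as the number of subjects with that outcome of interest during the Treatment Period divided by the total duration of treatment", with an on-study version alongside. Each subject adds at most one to the numerator. The interval is specified: "Exposure-adjusted incidence rates and associated exact CIs" "based on the Poisson distribution will be calculated for each treatment group and reported per 100 patient-years".
- **Event-count rate.** The next paragraph says "Similar exposure-adjusted analysis will also be performed with the number of events as the numerator", over the same on-treatment or on-study exposure. No interval is named here.

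The section's outcomes include "Incidences of renal-related and kidney stone TEAEs and SAEs", which can occur more than once in a subject. A later paragraph says "Estimates of treatment differences with corresponding 95% CIs will be calculated" and leaves the choice of method to the SAP: "The appropriate approaches may depend on the number of events observed during blinded data review".

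Section 9.4.2.4 extends the approach to TEAEs, SAEs and TEAEs leading to permanent discontinuation: "Similar methods will be applied for estimating proportions and exposure-adjusted incidence rates". Section 9.4.2.3 does the same for MACE and MACE+. Overdispersion, robust variance, negative-binomial models and the bootstrap are not mentioned. The document supplied contains no separate SAP text on this point.

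**The concern.** A Poisson interval assumes that the variance of the total count equals its mean. That is reasonable for uncommon outcomes counted once per subject. It fails when some subjects are more prone to events than others, or when one event makes another more likely. The total then varies more than a Poisson count, and an interval built on the Poisson variance is too short.

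A programmer following section 9.4.2.2 would find only one interval method for these rates and would probably apply it to both numerators. The per-arm event rates for all TEAEs, and for renal-related or kidney stone AEs if repeats occur, would then look better known than they are. The study's primary objective is to characterise safety, so an interval labelled 95% should cover at close to that level.

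**Working it through.** **Plan figure.** The protocol gives no precision figure for event rates. Its safety precision figure, in section 9.2, is for eCrCl change. It reproduces, 1.96 × 10 × √(2/300) = 1.60 mL/min, and this point does not touch it.

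**Inputs from the protocol.** There are 300 subjects per arm (section 4.1), 95% intervals (section 9.1), and 24 months of 28 days (section 8). Full follow-up is 24 × 28 / 365.25 = 1.84 years per subject, or 300 × 1.84 = 552 patient-years per arm.

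**Assumed inputs.** The mean number of events per subject (μ) and the negative-binomial shape (k) are not in the documents. A range is shown. Equal exposure across subjects is also assumed.

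**Formulas.**
- Exact Poisson limits for a count x: χ²(0.025; 2x)/2 and χ²(0.975; 2x+2)/2, each divided by patient-years.
- Variance/mean ratio of the count: 1 + μ/k. The correct interval is wider by about √(1 + μ/k).
- Subject-level robust interval on the log scale: rate × exp(±1.96 × √V / x), where V is 300 times the sample variance of the per-subject counts.

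**Simulated coverage of nominal 95% intervals** (20,000 arms of 300):

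| μ per subject | k | Variance/mean | Width factor | Exact Poisson | Robust |
|---|---|---|---|---|---|
| 4 | 1 | 5.0 | 2.24 | 62% | 95% |
| 3 | 1 | 4.0 | 2.00 | 68% | 95% |
| 3 | 2 | 2.5 | 1.58 | 79% | 95% |
| 0.1 | 0.1 | 2.0 | 1.41 | 85% | 94% |
| 0.05 | 0.1 | 1.5 | 1.22 | 91% | 95% |
| 0.1 | 0.5 | 1.2 | 1.10 | 93% | 95% |
| 0.05 | 1 | 1.05 | 1.02 | 96% | 95% |
| 0.02 | 0.1 | 1.2 | 1.10 | 95% | 97% |
| 0.01 | 0.1 to 1 | 1.01 to 1.1 | 1.00 to 1.05 | 98% to 99% | 90% to 92% |

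Separate runs of the same settings differ by about one percentage point. Over 1.84 years, 3 to 4 events per subject is about 163 to 217 per 100 patient-years (all-TEAE scale), and 0.05 to 0.1 is about 2.7 to 5.4.

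In the last row the robust interval is undefined for arms with zero events (5% to 6% of arms), and these are counted as not covered. That accounts for most of its shortfall.

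**A second model** draws the affected subjects first and then the events within them, with 9 to 75 affected subjects per arm. Exact Poisson coverage is 91% to 94% at a mean of 1.25 events per affected subject, 88% to 91% at 1.5, 81% to 85% at 2 and 73% to 76% at 3. The correct interval is about 1.1 to 1.9 times as wide.

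**Worked example (invented data).** Take 300 subjects and 500 patient-years, with 20 affected subjects: 14 with one event, 3 with two, 2 with three and 1 with four.
- Events: 14 + 6 + 6 + 4 = 30, a rate of 6.0 per 100 patient-years.
- Exact Poisson interval: 4.05 to 8.57.
- Sum of squared counts: 14 + 12 + 18 + 16 = 60. V = (60 − 30²/300) × 300/299 = 57.2, so V/30 = 1.91.
- Robust interval: 6.0 × exp(±1.96 × √57.2/30) = 3.66 to 9.83.
- Widths: 6.17 against 4.52, so the robust interval is about 37% wider.

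**The case against.** The strongest reply is that the protocol never says exact Poisson intervals will be used for event counts. The event-count sentence names no interval, and its back-reference attaches most directly to the exposure denominators. Section 9 promises further detail in the SAP. This stands: the carry-over is an inference. It is still the natural one, because no other method is offered. If it is wrong, the interval is simply unspecified and the same sentence would settle it.

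A reader might go further and infer that chance differences between arms will be reported as signals. The documents do not support that. The Poisson sentence covers intervals within each treatment group, and section 9.4.2.2 expressly leaves the method for treatment differences to the SAP. That deferral follows the sentence on treatment differences, so it does not clearly settle the per-arm intervals either.

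A reader might also infer that every safety outcome is affected. Only section 9.4.2.2 mentions an event numerator; sections 9.4.2.3 and 9.4.2.4 import it by reference to similar methods. No repeat-episode count is defined for creatinine elevations. MACE is too sparse for the problem to matter, and its Cox analysis uses first occurrence. Section 1.2.1 puts renal-related serious TEAEs at no more than 1% in Phase 3; at 0.01 events per subject the exact interval is conservative.

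Finally, the size depends on the assumed dispersion. At k of 0.5 to 1, coverage at 0.05 to 0.1 events per subject is 93% to 96%, which few would contest. Replacing exact Poisson everywhere would also do harm, because the robust interval fails for arms with zero events.

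**Conclusion.** The point holds within limits. As most naturally read, section 9.4.2.2 puts exact Poisson intervals on event counts that may include repeats, and these are too narrow per arm for outcomes that recur often. Under the assumed negative-binomial counts, coverage is about 62% to 79% at 3 to 4 events per subject, about 84% to 96% at 0.05 to 0.1 per subject, and near or above 95% for sparse outcomes. All these figures rest on assumed event means and dispersion.

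The consequence is modest. Section 9.4.2 calls the safety analyses descriptive and makes eCrCl change the main estimand; the event-count rates are an addition. The eCrCl MMRM, the Wilson intervals for proportions, the subject-count rates and the Cox analysis of MACE are unaffected. It is worth settling before database lock because the remedy is simple and restores coverage to about 94% to 95% where the shortfall occurs.

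**What to change.** Add to section 9.4.2.2, or to the SAP before database lock:

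- Event-count rates for outcomes with repeat events (all TEAEs, and renal-related or kidney stone AEs when repeats occur) use a subject-level robust variance or a negative-binomial model with log exposure as offset.
- Any between-arm comparison of event-count rates uses the same variance.
- Exact Poisson intervals are kept for subject-count rates, and for event-count rates with zero or few events or with no repeats.
- The cut-off for few events is stated in advance and applied to blinded pooled counts, so that both arms get the same method. As a guide, at 0.02 events per subject (about 6 expected events per arm) exact Poisson coverage was 94% to 95% even with k = 0.1.

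Sections 9.4.2.3 and 9.4.2.4 then follow by their existing references. The cost is a few lines of text, a little more programming and wider intervals for the recurrent outcomes. No new data are needed.
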